7.1 Definition of primary endpoint

Pain relief will be assessed at 15, 30, 45, 60, and 90 minutes, and at 2, 3, 4, 5, 6, 7, 8, and 16 hours after first dose using a 5-point verbal rating scale (VRS) with categories 0 (none), 1 (a little), 2 (some), 3 (a lot), or 4 (complete) (see Section 12.2.1.2).

The primary endpoint of the trial will be 4-hour Total Pain Relief (TOTPAR4). TOTPAR4 is a time-weighted measure of AUC up to 4 hours and is a summary measure that integrates serial assessments of a subject's pain over the duration of 4 hours after first dose.

TOTPAR4 scores will be calculated as $\sum PR_{t=4} \times [\text{time (hours) elapsed since previous observation}]$ where $PR_{t=4}$ is the Pain Relief at time point $t = 4$ in comparison to the assessment before administration of IMPs (Max and Laska 1991). For the first pain relief assessment, time (hours) elapsed since previous observation is time since first dose of IMP. Pain relief assessments after start of rescue medication intake (Section 10.5) will be set to missing and will be imputed as described in the statistical section (see Section 14.5.5).

Minimum and maximum potential value for TOTPAR4 are 0 and 16 points, corresponding to a value of 0 (none) or 4 (complete) at all pain relief assessments in the first 4 hours after first dose, respectively.

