14.5.4 Analysis of additional efficacy outcomes

The pain intensity scores (NRS) at all the time points (see Section 1.8) after the first dose of IMPs will be analyzed by an ANCOVA model with treatment, site, and baseline pain as covariates.

Pain relief expressed as Total Pain Relief after 6 hours and after 8 hours (TOTPAR6, TOTPAR8) will be analyzed with the same ANCOVA model and missing data handling as the primary analysis.

The specification of the statistical analysis of the following additional efficacy outcomes including statistical analysis models, formal statistical tests, and further specifications in detail will be provided in the statistical analysis plan:

- Pain intensity score reductions (Pain Intensity Difference [PID], NRS) for each time point after the first dose of IMPs.
- Summed Pain Intensity Difference (SPID) at 4, 6, 8, and 24 hours after the first dose of IMPs.
- Pain relief scores for each time point after the first dose of IMPs.

-
- Time to onset of first perceptible pain relief (Stopwatch 1).
 - Time to onset of meaningful pain relief (Stopwatch 2).
 - Time to achieve a 50% reduction in baseline pain (pain at least half gone).
 - Time to request the first dose of rescue medication.
 - Time to first intake of rescue medication.
 - Subject's global evaluation of the treatment (5-point Likert scale) 8 hours or before first intake of rescue medication (whatever the first) and 24 hours after the first dose of IMPs.

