8. EFFICACY ANALYSES

8.1 Efficacy Variables

8.1.1 Primary Efficacy Variable

The primary endpoint of the trial is 4-hour Total Pain Relief (TOTPAR4). TOTPAR4 is a time-weighted measure of Area under the Longitudinal Pain Relief Curve (AUC) up to 4 hours and is a summary measure that integrates serial assessments of a subject's pain over the duration of 4 hours after first dose (in [Appendix A](#)).

In general, the Total Pain Relief (TOTPAR) from the first administration of IMP to a fixed time-point, j , will be defined as:

$$\text{TOTPAR}_j = \sum W_i * \text{PR}_i, \text{ with } i \leq j$$

where the \sum sums over all observations collected from 0.25 hours after first IMP administration to Hour j and W_i is the time elapsed from the previous observation of pain relief PR_{i-1} to the current observation PR_i . For example, The TOTPAR4 will be calculated as a weighted sum of the observed pain relief scores for the first 4 hours after first dose with weights proportional to the duration of time since the last pain relief assessment.

For the first pain relief assessment, time (hours) elapsed since previous observation is time since first dose of IMP. Pain relief assessments after start of rescue medication intake will be set to missing and will be imputed as described in Section 8.3.

Minimum and maximum potential value for TOTPAR4 are 0 and 16 points, corresponding to a value of 0 (none) or 4 (complete) at all pain relief assessments in the first 4 hours after first dose, respectively.

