8.3 Handling of Dropouts or Missing Data

Diligent attempts will be made to limit the amount of missing data in the pain relief assessments used to determine the primary efficacy endpoint. Efforts will be made to encourage but not to enforce subjects to not start rescue medication intake if not needed. Assessments with missing date/time of evaluation will be considered unreliable and removed from all analyses and treated as missing values. Assessments made after the subject's first dose of rescue medication will be considered missing values and excluded from the analyses. Other than the methods outlined below for TOTPAR4, TOTPAR6, and TOTPAR8, no imputations will be performed to replace missing values for any of the other endpoints; those missing values will be left as missing.

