8.3.2 Sensitivity analysis of TOTPARs

For sensitivity analysis, missing and disregarded pain relief assessments will be imputed with the following two imputation methods:

2. LOCF Only
3. LOCF with Zero Substitution
 - LOCF for intermittent missing data;

- And substitution by zero for missing data after premature discontinuation from the trial or disregarded pain relief assessments after start of rescue medication intake.

While the sensitivity analyses below are not mentioned in the protocol, they are added to address the specific concern when rescue medication is given prior to the scheduled assessment time. Clearly, once rescue medication is given the pain levels will drop significantly and measurements post rescue medication are excluded from the analyses. The sensitivity analyses below will enable us to include subjects with rescue medication at the subsequent assessment time point.

4. WOCF with LOCF: Worst Observation Carried Forward (WOCF) is used to replace the scheduled pain relief assessments after the first intake of rescue medication, and LOCF is used to replace all other missing pain assessments. WOCF is defined as carrying forward the worst previous pain assessment, even if it is the baseline assessment.
5. WOCF Only

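### SAP 8.3 extends post-rescue deletion from pain relief to every score and imputes only TOTPAR, leaving by-time-point ANCOVAs to subjects not yet rescued, SPID without a missing-term rule, and the 16-hour NRS outside PID

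*SAP*

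**What the plan says.** **Deletion after rescue.** SAP 8.3 covers all assessments: those made after a subject's "first dose of rescue medication will be considered missing values and excluded from the analyses". Protocol 7.1 is narrower: "Pain relief assessments after start of rescue medication intake (Section 10.5) will be set to missing and will be imputed as described" in its missing-data section, 14.5.5, which also speaks of pain relief only.

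**Imputation.** SAP 8.3 imputes TOTPAR4, TOTPAR6 and TOTPAR8. For everything else, "no imputations will be performed to replace missing values for any of the other endpoints; those missing values will be left as missing".

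**Analyses that use these scores.** Protocol 14.5.4 states: "The pain intensity scores (NRS) at all the time points (see Section 1.8) after the first dose of IMPs will be analyzed by" an ANCOVA, with no exclusion for rescue. It leaves the detail of PID, SPID and pain relief by time point to the SAP. SAP 9.4 runs the primary ANCOVA model on pain relief, NRS and PID at each time point (exploratory). SAP 9.3 runs it on SPID4/6/8/24 (secondary).

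**SPID and the 16-hour score.** SPID is the sum of PID times hours since the previous observation (Protocol 12.2.1.4; SAP 8.1.2 and Appendix A item 6). Neither document says what happens when a PID is missing. NRS is collected at 16 hours (Protocol 1.8 note c; SAP Appendix A item 1). The PID lists in Protocol 12.2.1.4 and SAP Appendix A item 5 go from 8 to 24 hours, whereas Protocol 14.5.4 asks for "Pain intensity score reductions (Pain Intensity Difference [PID], NRS) for each time point after the first dose of IMPs".

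**What the SAP already does for TOTPAR.** SAP 8.3.2 adds analyses that "will enable us to include subjects with rescue medication at the subsequent assessment time point". It also specifies LOCF, and "substitution by zero for missing data after premature discontinuation from the trial or disregarded pain relief assessments after start of rescue medication intake". Both apply equally in all arms, but only to TOTPAR.

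**The concern.** Rescue is offered when trial medication gives insufficient relief (Protocol 10.5), so subjects not yet rescued at a late time point are a selected group. If one arm rescues more and rescue tracks pain, the weaker arm loses more of its poor responders and the difference usually shrinks. This works in both directions, so a worse arm can also look similar. Protocol 14.5.1 raises the same worry about subjects who discontinue early. Time points before 2 hours should change little, because subjects are encouraged to wait 120 minutes.

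For SPID the problem is a missing rule. One programmer could set SPID to missing when a term is missing. Another could sum the terms that exist, by analogy with TOTPAR, which "sums over all observations collected from 0.25 hours after first IMP administration". Both fit the text and they give different secondary results.

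At stake is the reading of the secondary SPID tables and the exploratory NRS, PID and pain relief tables. They are titled FAS, could rest on a subset, and might appear to disagree with TOTPAR for reasons unrelated to the drugs.

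**Working it through.** The plan gives no figure to reproduce here. Parts 1 and 2 are illustrations, because the documents give no rescue rates; means, SDs and correlations are assumed. The *true* difference means the difference if nobody took rescue. Part 3 is arithmetic on the documents' own times.

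**1. One time point, rescuers dropped.** Assume PID has SD 2.5, with mean 2 on monotherapy and 3 on the FDC (true difference 1.0). The tendency to rescue has correlation ρ with PID and a threshold common to both arms.

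- Control: rescued fraction p, a = normal quantile of p.
- FDC: a′ = a − ρ × 1.0/2.5, p′ = Φ(a′).
- Mean among those not rescued = μ + ρ × 2.5 × φ(a)/(1 − p).
- Mean with PID = 0 for rescuers = (1 − p) times that.

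Worked case, ρ = 0.5 and p = 40%:
- Control: a = −0.253, φ = 0.386; 2 + 1.25 × 0.386/0.60 = 2.805.
- FDC: a′ = −0.453, p′ = 32.5%, φ = 0.360; 3 + 1.25 × 0.360/0.675 = 3.667.
- Difference, rescuers dropped: 0.86. With PID = 0: 0.675 × 3.667 − 0.60 × 2.805 = 0.79.

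| ρ | Dropped (control rescue 20/40/60%) | PID = 0 (20/40/60%) |
|---|---|---|
| 0.3 | 0.96 / 0.95 / 0.94 | 0.87 / 0.73 / 0.55 |
| 0.5 | 0.90 / 0.86 / 0.83 | 0.89 / 0.79 / 0.65 |
| 0.7 | 0.82 / 0.73 / 0.68 | 0.89 / 0.84 / 0.75 |
| 1.0 | 0.64 / 0.47 / 0.35 | 0.84 / 0.87 / 0.90 |

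With equal rescue in both arms, dropping gives 1.00 (no bias) and PID = 0 gives 0.80/0.60/0.40. With rescue fixed at 60% against 30% and a true difference of 1.25, dropping gives 0.90 down to 0.08 and PID = 0 gives 1.45 down to 1.38 as ρ goes from 0.3 to 1.0. Zero substitution can therefore attenuate or exaggerate.

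**2. SPID, two readings.** Simulation with 150,000 per arm at the scheduled times from 0.25 to 8 hours. PID = (2 or 3 + subject effect, SD 2.0) × min(t/2, 1) + residual, SD 1.5. Rescue follows the first time at or after 2 hours when PID plus subject-level noise is below 0. Noise SD of 0, 3 and 5 gives correlations of 1.0, 0.64 and 0.45. By 8 hours, 48–49% of control subjects and 31–42% of FDC subjects are incomplete.

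| Correlation | 1.0 | 0.64 | 0.45 |
|---|---|---|---|
| SPID8, true | 7.2 | 7.2 | 7.2 |
| SPID8, subject dropped | 3.6 | 5.9 | 6.6 |
| SPID8, observed terms summed | 6.8 | 6.3 | 5.7 |
| SPID8, LOCF | 8.1 | 7.6 | 7.3 |
| SPID4, true | 3.2 | 3.2 | 3.2 |
| SPID4, subject dropped | 2.0 | 2.7 | 2.9 |
| SPID4, observed terms summed | 3.0 | 3.0 | 2.8 |

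Reruns with other seeds agree to about 0.1. After rescue no later term is observed, so summing the observed terms amounts to setting every later PID to 0. The better of the two readings changes with the correlation.

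**3. SPID24 weights.** On the written PID list the last interval is 24 − 8 = 16 hours, so the 24-hour PID carries 16/24 = 67%. With the 16-hour score, the last two intervals are 8 hours each, or 8/24 = 33% each. The versions differ by 16·PID24 − (8·PID16 + 8·PID24) = 8 × (PID24 − PID16): 8 SPID points for each NRS point of change between 16 and 24 hours.

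**The case against.** Much of SAP 8.3 is within its authority. Deleting post-rescue pain relief follows Protocol 7.1, and Protocol 14.5.4 hands PID, SPID and pain relief by time point to the SAP. That stands: for pain relief by time point only a rescuer-inclusive analysis is lacking. For NRS, a reader might infer that the SAP contradicts the protocol. The protocol names the time points and is silent on rescue, so this is an unlisted extension rather than a contradiction. The SAP does not hide the exclusion: section 11 mentions it as background to other changes, but does not list its extension to NRS.

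The affected analyses are secondary or exploratory without multiplicity adjustment, and the summaries report the number of non-missing observations, so shrinking denominators would be visible. This limits the consequence but does not supply the SPID rule.

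The sizes are also unknown. At correlations of 0.3 to 0.5 and 20–40% control rescue, dropping rescuers keeps 0.86 to 0.96 of a true 1.0. The striking values need near-perfect correlation or heavily unequal rescue. At those modest correlations zero substitution is further from the no-rescue difference, so it cannot be presented as the correction.

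Omitting 16 hours may be deliberate, since that score is self-recorded at home and both PID lists agree. No reason is given, however.

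**Conclusion.** The point holds as a gap to close before unblinding. On the text alone: the deletion is extended to NRS without being listed as a change, the by-time-point ANCOVAs rest on subjects not yet rescued, SPID4/6/8/24 has no missing-term rule, and the 24-hour score weighs 67% instead of 33% in SPID24 under the PID lists. Any bias depends on rescue differing by arm and tracking pain; its size cannot be known from the documents.

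Four stronger readings are not supported:
- **That the trial's conclusion is at risk.** TOTPAR4/6/8 have their own imputation, and success rests on TOTPAR4.
- **That the SAP drops rescued subjects from SPID.** It does not say so; the text leaves both computations open.
- **That hours 8 to 16 vanish from SPID24.** This would need the weight to run from the 16-hour NRS while its PID is left out. By analogy with TOTPAR in SAP 8.1.1, where the weight runs from the previous observation in the same sum, the 24-hour score gets 16 hours.
- **That rescue users lose their 24-hour global rating.** SAP 8.3 read literally would remove it, but SAP 9.3 and Appendix A item 8 schedule it without a rescue condition, and the specific rule would normally govern.

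**What to change.** Before unblinding:

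1. **16-hour score.** Include the 16-hour NRS in PID and SPID24, or state why it is left out. Reconcile Protocol 12.2.1.4 and SAP Appendix A item 5 with Protocol 14.5.4. The downside of including it is that it is self-recorded at home.
2. **SPID.** Fix one rule for terms after rescue that keeps rescued subjects in the FAS analysis, for example LOCF for intermittent gaps with a post-rescue substitution equal in all arms. Report the other SAP 8.3.2 method (LOCF or zero substitution) as sensitivity.
3. **By-time-point tables.** Label them as subjects not yet rescued. For NRS and PID add a rescuer-inclusive version using the SAP 8.3.2 methods, without making zero substitution the main analysis.
4. **SAP section 11.** List the extension of the deletion rule from pain relief to NRS.

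Optionally, add one line confirming that the 24-hour global rating is kept for rescue users.

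The cost is SAP wording, some programming, a reconciling note to the protocol and a few extra tables, each resting on a single-imputation assumption. No new data are needed.

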8.3.1 Analysis of TOTPARs

For the primary endpoint TOTPAR4, as well as for secondary endpoints TOTPAR6 and TOTPAR8, missing pain relief assessments as well as pain relief assessments after start of intake of rescue medication, will be imputed according to the following methods:

1. LOCF with Delta Substitution
 - Last Observation Carried Forward (LOCF) for intermittent missing data and substitution by δ for missing data after premature discontinuation from the trial or disregarded pain relief assessments after start of rescue medication intake. The value of parameter δ will depend on the reason for discontinuation and treatment arm. The following 3 categories of reason for discontinuation will be distinguished: Discontinuation due to Lack of Efficacy (LoE), adverse events, and other, non-drug related reasons. The parameter will be:
 - $\delta = 0$: For missing data after discontinuation due to LoE, discontinuation due to adverse events and for disregarded pain relief assessments after start of rescue medication intake for subjects in the tramadol HCl/diclofenac sodium FDC combination arms
 - $\delta = 0.375$: For missing data after discontinuation due to LoE, discontinuation due to adverse events and for disregarded pain relief assessments after start of rescue medication intake for subjects in the monotherapy arms diclofenac sodium 50 mg and tramadol HCl 50 mg
 - $\delta = 0$: For missing data after discontinuation due to other, non-drug related reasons

8.3.2 Sensitivity analysis of TOTPARs

For sensitivity analysis, missing and disregarded pain relief assessments will be imputed with the following two imputation methods:

2. LOCF Only
3. LOCF with Zero Substitution
 - LOCF for intermittent missing data;

- And substitution by zero for missing data after premature discontinuation from the trial or disregarded pain relief assessments after start of rescue medication intake.

While the sensitivity analyses below are not mentioned in the protocol, they are added to address the specific concern when rescue medication is given prior to the scheduled assessment time. Clearly, once rescue medication is given the pain levels will drop significantly and measurements post rescue medication are excluded from the analyses. The sensitivity analyses below will enable us to include subjects with rescue medication at the subsequent assessment time point.

4. WOCF with LOCF: Worst Observation Carried Forward (WOCF) is used to replace the scheduled pain relief assessments after the first intake of rescue medication, and LOCF is used to replace all other missing pain assessments. WOCF is defined as carrying forward the worst previous pain assessment, even if it is the baseline assessment.
5. WOCF Only

8.4 Interim Analysis and Data Monitoring

No interim analyses are planned for evaluating efficacy.

8.5 Examination of Subgroups

Subgroup analyses are to be performed for the primary efficacy variable with subjects categorized by levels of baseline pain severity. Furthermore, primary and secondary TOTPAR analyses will be conducted by site.

8.6 Multiple Comparisons/Multiplicity

Testing multiple hypotheses may increase the family-wise type I error rate, the probability to erroneously reject at least 1 true null hypothesis, beyond the pre-specified significance level. In order to control the family-wise type I error rate in the strong sense at the pre-specified 1-sided significance level of $\alpha = 2.5\%$, a Bonferroni-Holm procedure (Holm 1979) will be used. The details will be explained later in Section 9.1 of this SAP.

8.7 Multicenter Studies

The study will be conducted at approximately 8 investigational sites in Mexico, about 1065 subjects are planned to be enrolled (i.e., sign the informed consent) in order to allocate 800 subjects to IMP, i.e., about 130 subjects per trial site in approximately 8 sites.

The site will be included as a covariate in the multivariate analysis. If a highly influential site is identified, the differences between treatment groups might be examined with and without the influential site.

9. METHODS OF EFFICACY ANALYSIS

The primary analysis to investigate the primary objective of the trial is based on the primary efficacy endpoint (TOTPAR4) and will be performed on the FAS and repeated as sensitivity analysis on the PPS. Additional sensitivity analyses and the analysis of additional efficacy parameters will be performed on the FAS, unless otherwise specified.

9.1 Primary Efficacy Analyses

The primary endpoint will be TOTPAR4 and the primary analysis performed on the FAS. The TOTPAR4 will be calculated as a weighted sum of the observed pain relief scores during the first 4 hours after first dose with weights proportional to the time since the last pain relief assessment. TOTPAR scores can be interpreted as estimates of the area under the longitudinal pain relief curve. TOTPAR4 will be displayed for each treatment group by study visit using summary statistics, including the number of observations, the mean, Q1, median, Q3, standard deviation (SD), and range (min, max).

The estimate of interest for the primary efficacy analysis is the difference in the primary efficacy endpoint in all subjects in the FAS attributable to the initially allocated trial medication. The FAS analysis will be the primary analysis for all comparisons. The primary objective of the trial is investigated by 4 formal statistical tests (see Table 1). Testing multiple hypotheses, however, may increase the family-wise type I error rate, the probability to erroneously reject at least 1 true null hypothesis, beyond the pre-specified significance level. In order to control the family-wise type I error rate in the strong sense at the pre-specified 1-sided significance level of $\alpha = 2.5\%$, a Bonferroni-Holm procedure will be used. The elementary null hypotheses H_{01} , H_{02} , H_{03} , and H_{04} and according statistical tests T_1 , T_2 , T_3 , and T_4 of the primary objective of the trial are listed in Table 1.

Table 1: Statistical tests and null hypotheses (all 1-sided) of the primary objective of the trial

Test	Description	Null Hypothesis	Alternative Hypothesis
T_1	Superiority of tramadol HCl/diclofenac sodium 50 mg/50 mg vs. tramadol HCl 50 mg	$H_{01}: \mu_{T50} - \mu_{ADL50/50} \geq 0$	$H_{A1}: \mu_{T50} - \mu_{ADL50/50} < 0$
T_2	Superiority of tramadol HCl/diclofenac sodium 50 mg/50 mg vs. diclofenac sodium 50 mg	$H_{02}: \mu_{D50} - \mu_{ADL50/50} \geq 0$	$H_{A2}: \mu_{D50} - \mu_{ADL50/50} < 0$
T_3	Non-inferiority of tramadol HCl/diclofenac sodium 25 mg/25 mg vs. tramadol HCl 50 mg	$H_{03}: \mu_{T50} - \mu_{ADL25/25} \geq \Delta$	$H_{A3}: \mu_{T50} - \mu_{ADL25/25} < \Delta$
T_4	Non-inferiority of tramadol HCl/diclofenac sodium 25 mg/25 mg vs. diclofenac sodium 50 mg	$H_{04}: \mu_{D50} - \mu_{ADL25/25} \geq \Delta$	$H_{A4}: \mu_{D50} - \mu_{ADL25/25} < \Delta$

ADL Adorlan (tramadol HCl/diclofenac sodium); D diclofenac sodium; T tramadol hydrochloride; HCl hydrochloride. $\Delta = 1.5$ is the non inferiority margin.

The trial will be positive if at least 1 of the according 4 statistical tests rejects the according null hypothesis.

According to the Bonferroni-Holm procedure, the p-values of the 4 tests T_1 , T_2 , T_3 , and T_4 will be sorted in ascending order $p_{(1)} < p_{(2)} < p_{(3)} < p_{(4)}$ and the following algorithm will be applied to the corresponding null hypotheses $H_{(01)}$, $H_{(02)}$, $H_{(03)}$, $H_{(04)}$:

- Step 1. If $p_{(1)} < \alpha/4$ (0.625%), reject $H_{(01)}$ and move to the next step. Otherwise retain all null hypotheses and stop.
- Step 2. If $p_{(2)} < \alpha/3$ (0.833%), reject $H_{(02)}$ and move to the next step. Otherwise retain $H_{(02)}$, $H_{(03)}$ and $H_{(04)}$ and stop.
- Step 3. If $p_{(3)} < \alpha/2$ (1.25%), reject $H_{(03)}$ and move to the next step. Otherwise retain $H_{(03)}$ and $H_{(04)}$ and stop.
- Step 4. If $p_{(4)} < \alpha$ (2.5%), reject $H_{(04)}$ and move to formally testing null hypotheses related to secondary endpoints. Otherwise retain $H_{(04)}$.

The primary analysis will use an ANCOVA model with treatment, site, and baseline pain (measured on an 11-point NRS) as covariates. The pain intensity score assessed before IMP intake will be considered the baseline pain intensity and site will be used as a covariate.

